3.1 Hypothesis

Patients treated with bryostatin will experience a greater improvement in cognitive function as measured by the SIB from baseline to the primary efficacy endpoint after two 12 week courses of treatment, as compared to patients on placebo during the same time period. The null hypothesis will be rejected at a significance level of a two-sided $\alpha = 0.05$. The test of the null hypothesis will be a superiority test based on the treatment difference in Week 28 SIB from baseline means as assessed by general estimating equations (GEE) regression, and only an improvement in the SIB score from baseline is of clinical significance.

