9.4 Analysis of Primary Efficacy Endpoint

The treatment difference in the primary efficacy endpoint of total SIB scores from baseline at Week 28 will be determined from a regression model that utilize SIB values taken at Weeks 0, 5, 9, 13, 15, 20, 24, 28 and 30. As SIB is a continuous outcome measure, a regression model will be used to estimate the treatment difference in mean SIB from baseline at Week 28. Both linear and non-linear terms will be considered in these regression models. Since correlation of SIB measures over time within a patient will be present, regression coefficients will be estimated using the generalized estimating equations (GEE) methodology.¹⁸ GEE regression models are used to appropriately estimate the population average effects from a sample of individuals when the correlations of SIB measures within individuals are unknown. The GEE method accounts for the correlation structure in the model. However, the estimates of model coefficients and their standard errors models are unbiased even if the working correlation model is incorrectly specified. The primary analysis will be conducted on FAS population. The PP and CAS populations will be used as supportive analyses. All statistical tests for efficacy will be two-sided tests, with $\alpha=0.05$.

Based on the review of patients not treated with memantine in the NTRP 101-203 clinical trial, the expected number of patients who will drop out of the study prematurely will not be significant. However, missingness will be accounted for using weighted GEE methods.¹⁹ The GEE regression models will be carried out in SAS/STAT PROC GEE version 13.2. This SAS procedure will allow for implementation of weighted GEE methodology that can account for data missing a random. One additional patient may be randomized for each patient who discontinues the study prior to the primary endpoint (Week 28, Day 196).

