6.11.2 Primary Efficacy Analysis

The primary efficacy analysis will be performed using linear mixed model with repeated measures (MMRM) with SIB measured at baseline as covariate, visit treated as a continuous as well as categorical variable, treatment and treatment by visit interaction. Categorical visit will be used to identify the ordering of measurements within a subject, while continuous visit will be used as covariate alone as well as in interaction with treatment.

Week of planned visits will be used as values of categorical variable of visit. Actual study day of visits (calculated in weeks) will be used as values of continuous variable of visit. The dependent

QMD Ref: Worldwide-TMP-ST-005-7.0 Effective: 12Aug2019	Governing QMD: Worldwide-SOP-ST-001
Confidentiality Statement	
This document is the property of Worldwide Clinical Trials Inc. and may not be duplicated, copied, altered or removed from company without prior approval from Worldwide Quality Assurance or in compliance with Worldwide Standard Operating Procedures.	

Worldwide Clinical Trials Controlled Quality Management Document		
 WORLDWIDE CLINICAL TRIALS	Sponsor:	Synaptogenix, Inc.
	Protocol Number:	NTRP-101-204
STATISTICAL ANALYSIS PLAN. PHASE 2-3-4		

variable will be the change from baseline in SIB total score at weeks 5, 9, 13, 15, 20, 24, 28, and 30.

Correlation between repeated observations within a subject will be accounted for by specifying an unstructured correlation. If this model does not converge then the following covariance matrices will be used in this particular order until the model converges: Toeplitz, compound symmetry, and first-order autoregressive.

Analysis will be performed using PROC MIXED in SAS, and the resulting F-tests will be based on using Kenward-Roger’s adjusted degrees of freedom.

The treatment groups will be compared at all timepoints using a two-sided test at a 5% significance level, with the primary comparison being the difference in group means of SIB from baseline at Week 28.

The sample SAS code below implements the model detailed above with an unstructured covariance matrix (TYPE = UN in the REPEATED statement). The code assumes that AVISITN has 8 values (one for each post-baseline visit), and TRT01PN representing treatment is coded as 1 = bryostatin, 2 = placebo.

```
proc mixed data = ;
  class subjid trt01pn avisitn;
  model sibdiff = sibbase trt01pn avisitd trt01pn* avisitd /
ddfm = kr outpred = pred;

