  repeated avisitn / type = un subject = subjid;
  estimate "Bryostatin vs Placebo at week 28" trt01pn 1 -1
trt01pn* avisitd 28 -28 / cl;
run;
```

Variables names:

- subjid – unique number of subject,
- avisitn – visit as categorical variable,
- avisitd – visit as continuous variable,
- sibase – SIB at baseline,

QMD Ref: Worldwide-TMP-ST-005-7.0 Effective: 12Aug2019	Governing QMD: Worldwide-SOP-ST-001
Confidentiality Statement	
This document is the property of Worldwide Clinical Trials Inc. and may not be duplicated, copied, altered or removed from company without prior approval from Worldwide Quality Assurance or in compliance with Worldwide Standard Operating Procedures.	

Worldwide Clinical Trials Controlled Quality Management Document		
 WORLDWIDE CLINICAL TRIALS	Sponsor:	Synaptogenix, Inc.
	Protocol Number:	NTRP-101-204
STATISTICAL ANALYSIS PLAN. PHASE 2-3-4		

sibdiff – SIB difference from baseline,

trt01pn – treatment group.

As a sensitivity analysis the same model but using only categorical visit will be used. The following SAS code implements this model (the variable designations are the same):

```
proc mixed data = ;
  class subjid trt01pn avisitn;
  model sibdiff = sibbase trt01pn avisitn trt01pn* avisitn /
ddfm = kr outpred = pred;
  repeated avisitn / type = un subject = subjid;
  estimate "Bryostatin vs Placebo at week 28" trt01pn 1 -1
trt01pn* avisitn 0 0 0 0 0 0 1 0 0 0 0 0 0 0 -1 0 / cl;
run;
```

Patients that have missing SIB outcome data will be included in the primary analysis if they have complete SIB data for at least one follow-up timepoint (i.e., available case analysis). Although there is no universally acceptable, adequate method for analyzing longitudinal clinical trial data under ITT with missing primary endpoints, the available case analysis using a generalized linear mixed model approach such as MMRM will produce unbiased estimates of the treatment effect if the missingness is ignorable (i.e. missing completely at random or missing at random)^{2,3}.

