9 CHANGES TO PLANNED PROTOCOL ANALYSIS

1. The control of false discovery rate (FDR) excluded because it was planned for the secondary (not primary) endpoints and this is a phase 2 study.
2. For the 4th secondary endpoint: <The changes from baseline at Weeks 5, 9, 13, 15, 20 and 24 in the SIB total score for subjects with baseline MMSE-2 scores of 10-14 and 15-18> the list of visits changed from Weeks 9, 15, 20 and 24 to Weeks 9, 20, 24 and 30.
3. For efficacy analysis the GEE models replaced with MMRM models as more suitable approach for analysis of longitudinal data in neurology studies.

QMD Ref: Worldwide-TMP-ST-005-7.0 Effective: 12Aug2019	Governing QMD: Worldwide-SOP-ST-001
Confidentiality Statement	
This document is the property of Worldwide Clinical Trials Inc. and may not be duplicated, copied, altered or removed from company without prior approval from Worldwide Quality Assurance or in compliance with Worldwide Standard Operating Procedures.	

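### The primary Week 28 contrast is read off a straight line fitted to Weeks 5-30, so it equals the stated Week 28 difference in means only if the between-arm difference is close to linear in time

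*SAP*

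**What the plan says.** Protocol 3.1 sets a superiority test "based on the treatment difference in Week 28 SIB from baseline means", assessed by GEE regression. SAP 6.11.2 describes "the primary comparison being the difference in group means of SIB from baseline at Week 28".

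The primary model in SAP 6.11.2 has baseline SIB, treatment, continuous time and treatment by continuous time as fixed effects: "continuous visit will be used as covariate alone as well as in interaction with treatment". Categorical visit enters only the REPEATED statement, where it orders the measurements for "specifying an unstructured correlation". The fit uses Weeks 5, 9, 13, 15, 20, 24, 28 and 30. The ESTIMATE statement adds the treatment contrast to 28 times the slope contrast: "trt01pn* avisitd 28 -28 / cl".

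On the alternative, the SAP says: "As a sensitivity analysis the same model but using only categorical visit will be used". This model has its own code, table and figure (14.2.1.5).

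Protocol 9.4 says of the regression: "Both linear and non-linear terms will be considered in these regression models". SAP section 9 records "For efficacy analysis the GEE models replaced with MMRM models", but not that the primary model has no non-linear term.

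**The concern.** The target is a mean difference at one visit. The estimator borrows from all eight visits and forces the between-arm difference onto a straight line. If the true difference bends, the reported estimate and its 95% interval do not describe Week 28.

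The design gives reasons to check linearity. There are two courses with a gap between them. By Protocol Table 1, Weeks 15 and 30 fall four weeks after the latest dose, and the other six efficacy visits fall two weeks after. The objectives ask whether effects last.

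The PP and completer analyses (SAP 6.11.3) use the primary model, and the visit-specific and exploratory analyses (6.11.4.3, 6.11.4.4, 6.11.5) refer back to it. The categorical model would reveal a departure. No rule says what follows if the two models disagree, so the linear result would stand.

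**Working it through.** **The plan's own figure.** SAP section 4, Eq 1, with sigma 5.3, rho 0.5, n = 8, time variance 127 and 50 per arm: SE of the slope difference = sqrt(2 x 5.3² x 0.5 / (50 x 8 x 127)) = 0.0235. Power for 0.15 per week = Φ(0.15/0.0235 - 1.96), above 99.99%. With 40 per arm the SE is 0.0263 and power is 99.99%. The stated >99% reproduces, but it is power for a slope difference under linearity and says nothing about the Week 28 contrast if linearity fails.

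**Weights.** For complete data at planned times, the contrast is a weighted sum of the visit-specific differences. Under exchangeable covariance the weight at week t is 1/8 + (28 - 18)(t - 18)/568, where 18 is the mean of the eight weeks and 568 their sum of squared deviations. Week 28: 0.125 + 100/568 = 0.301. Week 30: 0.125 + 120/568 = 0.336. All eight, in order: -0.10, -0.03, 0.04, 0.07, 0.16, 0.23, 0.30, 0.34. Under AR(1) by visit order with r from 0.3 to 0.9, Week 28 gets 0.20-0.26 and Week 30 gets 0.40-0.64. With an unstructured fit the weights also vary between trials: 0.17-0.43 for Week 28 (5th to 95th percentile of 4,000 simulated covariance estimates, true covariance exchangeable).

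**Standard errors, 50 per arm.** Two readings of 5.3 are carried through.
- *5.3 is the SD of the score.* Conditioning on baseline with correlation 0.5 leaves 5.3² x (0.5 I + 0.25 J), an SD of 5.3 x sqrt(0.75) = 4.59. Linear: sqrt((2/50)(14.045 x 0.301 + 7.02)) = 0.671. Categorical: 4.59 x sqrt(2/50) = 0.918. Ratio 1.37.
- *5.3 is the residual SD at each visit, correlation 0.5.* Linear: sqrt((2/50)(14.045 x 0.301 + 14.045)) = 0.855. Categorical: 1.06. Ratio 1.24.

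Under AR(1) with SD 5.3 the ratio is 1.05-1.48.

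**Assumed profiles.** The documents give none. The true Week 28 difference is 4 in each.
- *Constant or linear:* 4.00, no bias.
- *A quarter lost at Weeks 15 and 30:* 4 - 1 x (0.072 + 0.336) = 3.59. RMSE, sqrt(bias² + SE²), is 0.79 linear against 0.92 categorical at SD 4.59, and 0.95 against 1.06 at SD 5.3.
- *Half lost at Weeks 15 and 30:* 4 - 2 x 0.408 = 3.18. Bias/SE is 0.817/0.671 = 1.22 or 0.817/0.855 = 0.96, so coverage is 77% or 84%. RMSE is 1.06 against 0.92, or 1.18 against 1.06.
- *Linear rise to 4 at Week 13, then flat:* the shortfalls of 2.46 at Week 5 and 1.23 at Week 9 carry negative weights, so the estimate is 4 + 2.46 x 0.104 + 1.23 x 0.033 = 4.30.
- *A difference of 2 in the first course and 4 in the second:* 4.06, almost no bias.

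Under exchangeable covariance, RMSE breaks even at a fractional loss of sqrt(0.918² - 0.671²)/(4 x 0.408) = 0.38 at Weeks 15 and 30. Power is little affected in the half-lost case: 99.7% linear against 99.2% categorical at SD 4.59. The damage is to the estimate and interval.

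**The case against.** The strongest reply is that a regression-based Week 28 estimate was the design from the start. Protocol 3.1 ties the test to GEE regression, Protocol 9.4 takes the Week 28 difference from a model using visits up to Week 30, the sample-size sections assume a slope, and Appendix 3 records that Week 30 was added deliberately. The SAP has precedence, and a promise to consider non-linear terms is not a promise to include them. All of this stands. The missing entry in SAP section 9 is therefore a minor documentation gap, and a reader should not infer an improper departure from the protocol. It does not make the fitted line equal the stated difference when the difference is curved.

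The second reply is efficiency. The linear model is more precise, and for mild waning it has the lower RMSE under exchangeable covariance. That stands too.

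Three stronger readings are tempting and not supported. First, that waning is expected: the objectives raise it only as a question, and Protocol 2.1.2.4 and 4.2 report differences in NTRP101-202 at the 30-day follow-up. Second, that the type I error is inflated: if the arms are identical at every visit, the contrast is unbiased. Third, that the test often rejects when Week 28 shows nothing. A difference of 4 at Weeks 20 and 24 only gives 1.56 and rejection in 64% (SD 4.59) or 45% (SD 5.3), but Week 28 has the same two-week spacing from a dose as those visits. That profile has no basis in the dosing schedule and is only an extreme illustration.

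**Conclusion.** The mismatch between the stated comparison and the primary estimator is real and follows from the printed code. Its consequence is conditional. If the difference is linear or constant over Weeks 5-30, the contrast is unbiased and the better choice. Otherwise it can understate or overstate Week 28: by about 0.8 of 4 points when half the effect is lost four weeks after dosing, or by 0.3 upwards for an early rise and plateau. These sizes rest on assumed profiles, exchangeable covariance, complete data and normal approximations. The pre-specified categorical model limits the harm but does not remove it, because it is only a sensitivity analysis. The change is worthwhile because it is cheap and the plan can afford the precision at its own SD.

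**What to change.** Make the categorical-visit MMRM already coded in SAP 6.11.2 the primary analysis and the linear-time model the sensitivity analysis. Swap Tables and Figures 14.2.1.4 and 14.2.1.5. Use the categorical model in 6.11.3, 6.11.4.3, 6.11.4.4 and 6.11.5, with Week 42 analysed only for subjects who completed that visit before it was removed. Record the change in SAP section 9 and in a protocol amendment, as Protocol section 9 requires for a change to the primary analysis.

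In 6.11.4.5 keep continuous time, since slopes are the endpoint there, but correct the code. VAR (absolute SIB or its change) is printed as a predictor of sibdiff and must be the response. The ESTIMATE statements use time and trt_no where the model uses avisitd and trt01pn. The cross-reference to the primary model needs revising.

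Dropping Week 30 from the line is not a substitute: under exchangeable covariance the half-lost profile gives 3.8, but the rise-and-plateau profile gives 4.5.

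No new data are needed. The cost is precision. For a 4-point linear or constant difference with 50 per arm, power goes from above 99.9% to 99.2% at SD 4.59, and from 99.7% to 96.5% at SD 5.3. With 20% dropout the categorical model has 97.4% or 92.1%. At larger assumed SDs with correlation 0.5 the loss matters more: 94% to 82% at SD 7, and 87% to 71% at SD 8.

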6.11.3 Supportive Analysis

Supportive sensitivity analysis for primary endpoint will be performed in the same manner as primary analysis, for PP and CAS populations.

Using MMRM for available cases as described in section 6.11.2 assumes that missingness in the SIB outcome measures is non-ignorable. However, at least some missing data at a given timepoint may be dependent on outcome values that are unobserved and therefore unmeasured, giving rise to non-ignorable missingness or missingness not at random (MNAR). Reasons for missing data will be recorded to help determine if missingness not at random is present. Determining the timing,

QMD Ref: Worldwide-TMP-ST-005-7.0 Effective: 12Aug2019	Governing QMD: Worldwide-SOP-ST-001
Confidentiality Statement	
This document is the property of Worldwide Clinical Trials Inc. and may not be duplicated, copied, altered or removed from company without prior approval from Worldwide Quality Assurance or in compliance with Worldwide Standard Operating Procedures.	

Worldwide Clinical Trials Controlled Quality Management Document		
 WORLDWIDE CLINICAL TRIALS	Sponsor:	Synaptogenix, Inc.
	Protocol Number:	NTRP-101-204
STATISTICAL ANALYSIS PLAN. PHASE 2-3-4		

frequency, and possible reasons for missing data is critical in helping to determine the underlying mechanism of the missed data, particular since all methods for handling missing data are based on unverifiable assumptions.³

If the reasons for missingness provides clinical evidence that MNAR is present, then sensitivity analyses that make reasonable assumptions about missing data will be performed. In the proposed sensitivity analyses, intermediate missed SIB values will be replaced with a ‘best’ case and ‘worst’ case, where the ‘best’ and ‘worst’ case SIB scores will be determined for each patient based on their observed data. In these sensitivity analyses, only intermediate missed SIB data will be filled in with the best- and worst-case values, giving rise to a monotonic missing data set. Under this scenario, it is reasonable to assume that data lost to follow-up is ignorable³.

6.11.4 Other Secondary Endpoints

Analysis of secondary efficacy endpoints will be conducted on the FAS population.

6.11.4.1 SIB total score at the Week 42 follow-up visit

This endpoint will be analyzed using an Analysis of Covariance (ANCOVA) model with SIB score at Week 42 as dependent variable; treatment group as factor, and baseline SIB total score, baseline MMSE-2 score, age and gender as covariates.

6.11.4.2 The change from baseline in SIB total score at Week 13

This endpoint will be analyzed using the same ANCOVA model as described in Section 6.11.6.1.

6.11.4.3 SIB total scores from baseline at Weeks 9, 20, 24 and 30

This endpoint will be analyzed using the same MMRM model as described in Section 6.11.2 with corrections for obtaining results on corresponding visits.

6.11.4.4 SIB total scores from baseline at Weeks 9, 20, 24 and 30 for subjects with baseline MMSE-2 scores of 10-14 and 15-18

This endpoint will be analyzed using the same MMRM model as described in Section 6.11.2 with additional fixed effect for grouped baseline MMSE-2 scores (10-14 and 15-18) and corrections for obtaining results on corresponding visits.

QMD Ref: Worldwide-TMP-ST-005-7.0 Effective: 12Aug2019	Governing QMD: Worldwide-SOP-ST-001
Confidentiality Statement	
This document is the property of Worldwide Clinical Trials Inc. and may not be duplicated, copied, altered or removed from company without prior approval from Worldwide Quality Assurance or in compliance with Worldwide Standard Operating Procedures.	

Worldwide Clinical Trials Controlled Quality Management Document		
 WORLDWIDE CLINICAL TRIALS	Sponsor:	Synaptogenix, Inc.
	Protocol Number:	NTRP-101-204
STATISTICAL ANALYSIS PLAN. PHASE 2-3-4		

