4.3.3 Secondary Efficacy Endpoints

- SIB score at the end of the Week 42 follow-up visit, for subjects who completed week 42
- The change from baseline (screening) SIB total score at week 13
- The changes from baseline at Weeks 9, 20, 24 and 30 in the SIB total score
- The changes from baseline at Weeks 9, 13, 20, 24 and 30 in the SIB total score for subjects with baseline MMSE-2 scores of 10-14 and 15-18
- SIB trends over time; individual-specific slopes of total SIB scores will be obtained for all patients.

CONFIDENTIAL

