9.5.1 SIB total score from baseline at the Week 42 follow-up visit

Treatment differences in SIB total score from baseline at Week 42, for subjects who completed that visit, will be estimated using an ANCOVA model that will adjust for baseline SIB total scores, baseline MMSE-2 scores, age, and gender.

9.5.2 SIB total score from baseline at Week 13

An ANCOVA model as described in Section 9.5.1 will be created to estimate the difference in SIB total scores at Week 13. Again, as with the SIB difference at Week 42. The ANCOVA model will adjust for baseline SIB, baseline MMSE-2 scores, age, and gender.

9.5.3 SIB total scores from baseline at Weeks 9, 20, 24 and 30

The linear regression models using the method of GEE as described in Sections 9.4 and 9.5.2 will be used to estimate the treatment difference in mean SIB total scores from the original baseline (i.e. at screening) at Weeks 9, 20, 24 and 30. As described in Section 9.4, weighted GEE will be used to account for data that are missing at random.

9.5.4 SIB total scores from baseline at Weeks 5, 9, 15, 20, and 24 for subjects with baseline MMSE-2 scores of 10-14 and 15-18

The estimation of the treatment differences at Weeks 9, 20, 24 and 30 for patients within each MMSE-2 group will be based on GEE linear regression model utilizing SIB total scores from baseline at these five time points. As described in Section 9.4, weighted GEE will be used to account for data that are missing at random.

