3.2 Secondary Endpoints

Secondary Efficacy Endpoints

- SIB score at the end of the Week 42 follow-up visit
- The change from baseline (screening) SIB total score at Week 13
- The changes from baseline at Weeks 5, 9, 15, 20 and 24 in the SIB total score
- The changes from baseline at Weeks 5, 9, 13, 15, 20 and 24 in the SIB total score for subjects with baseline MMSE-2 scores of 10-14 and 15-18
- SIB trends over time; individual-specific slopes of total SIB scores will be obtained for all patients.

Exploratory Endpoints

- Change from baseline in Alzheimer’s Disease Cooperative Study – Activities of Daily Living – Severe Impairment Version (ADCS-ADL-Sev) total score at Weeks 13 and 42
- Change from baseline in MMSE-2 total score at Weeks 13 and 42
- Change from baseline in Neuropsychiatric Inventory (NPI) total score at Weeks 13 and 42

Safety Assessments

- Treatment emergent adverse events (AEs) and serious adverse events (SAEs)
- Vital signs, hematology, blood chemistry, and physical examination including body weight
- Electrocardiogram (ECG) parameters
- Columbia Suicide Severity Rating Scale (C-SSRS)

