14.2.1.8	Mixed Model with Repeated Measures Analysis of Change from Baseline at week 28 in Severe Impairment Battery. Supportive Analysis: Per-Protocol Analysis Set	Stat IP	
14.2.1.9	Mixed Model with Repeated Measures Analysis of Change from Baseline at week 28 in Severe Impairment Battery. Supportive Analysis: Completers Analysis Set	Stat IP	
14.2.2	Secondary Efficacy Endpoints		
14.2.2.1	Analysis of Covariance model for Severe Impairment Battery at Week 42 follow-up visit	Stat IP	
14.2.2.2	Analysis of Covariance model for Change from Baseline of Severe Impairment Battery at Week 13	Stat IP	
14.2.2.3	Mixed Model with Repeated Measures Analysis of Changes from Baseline at weeks 9, 20, 24 and 30 in Severe Impairment Battery	Stat IP	
14.2.2.4	Mixed Model with Repeated Measures Analysis of Changes from Baseline at weeks 9, 20, 24 and 30 in Severe Impairment Battery for subjects with baseline MMSE-2 scores of 10-14 and 15-18	Stat IP	
14.2.2.5	Individual subject's trends of SIB over time	Stat IP	
14.2.2.6	Individual subject's trends of SIB changes from baseline over time	Stat IP	
14.2.3	Exploratory Endpoints		

QMD Ref: Worldwide-TMP-ST-005-7.0 Effective: 12Aug2019

Governing QMD: Worldwide-SOP-ST-001

Confidentiality Statement

This document is the property of Worldwide Clinical Trials Inc. and may not be duplicated, copied, altered or removed from company without prior approval from Worldwide Quality Assurance or in compliance with Worldwide Standard Operating Procedures.

Worldwide Clinical Trials Controlled Quality Management Document

**WORLDWIDE
CLINICAL TRIALS**

Sponsor:

Synaptogenix, Inc.

Protocol Number:

NTRP-101-204

STATISTICAL ANALYSIS PLAN. PHASE 2-3-4

Table Number	Table Title	Validation Method	Shell Number (if repeat)
14.2.3.1	Mixed Model with Repeated Measures Analysis of Change from Baseline at weeks 13 and 42 in Alzheimer’s Disease Cooperative Study – Activities of Daily Living - Severe Impairment Version	Stat IP	
14.2.3.2	Mixed Model with Repeated Measures Analysis of Change from Baseline at weeks 13 and 42 in Mini Mental State Examination, 2nd edition	Stat IP	
14.2.3.3	Mixed Model with Repeated Measures Analysis of Change from Baseline at weeks 13 and 42 in Neuropsychiatric Inventory	Stat IP	
14.3	Safety Data		
14.3.1	Displays of Adverse Events		
14.3.1.1	Overview of Adverse Events	IP	
14.3.1.2	Treatment Emergent Adverse Events	IP	
14.3.1.3	Patients with Treatment Emergent Adverse Events by Maximal Severity	IP	

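### SIB by MMSE-2 band is not planned for Week 28, the primary time point, and the SAP analysis drops Week 13 although it is a listed band endpoint

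*SAP*

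**What the plan says.** SAP 6.11.2 defines the primary analysis as a repeated-measures model fitted to change in SIB at Weeks 5 to 30, "with the primary comparison being the difference in group means of SIB from baseline at Week 28".

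A secondary endpoint looks at SIB within two baseline MMSE-2 bands, 10-14 and 15-18. Its visits are described differently from place to place:

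- Protocol 4.3.3: "The changes from baseline at Weeks 9, 13, 20, 24 and 30 in the SIB total score for subjects with baseline MMSE-2 scores" in the two bands.
- Protocol 9.5.4: the heading gives five weeks, the text gives four others in part, and the text then says the estimation "will be based on GEE linear regression model utilizing SIB total scores from baseline at these five time points".
- SAP 3.2: "The changes from baseline at Weeks 5, 9, 13, 15, 20 and 24 in the SIB total score for subjects with baseline MMSE-2" in the two bands.
- SAP 6.11.4.4: "SIB total scores from baseline at Weeks 9, 20, 24 and 30 for subjects with baseline MMSE-2 scores of 10-14 and 15-18".
- SAP Table 14.2.2.4: "Mixed Model with Repeated Measures Analysis of Changes from Baseline at weeks 9, 20, 24 and 30 in Severe Impairment Battery for subjects" in the two bands.

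SAP section 9, item 2, records a change of visits for this endpoint, ending at Weeks 9, 20, 24 and 30. SAP 6.11.4.4 says the primary model is reused with the band added as a fixed effect, and that output is adapted to the visits listed.

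**The concern.** For the whole trial population, leaving Weeks 13 and 28 out of the list of other visits (SAP 6.11.4.3) does no harm, because each has its own endpoint: Week 28 is primary and Week 13 is a separate secondary. The same four weeks are used for the bands, where nothing else covers those two visits. The Week 28 analyses, including the per-protocol, completer and categorical-visit versions, are not split by band. The Week 13 ANCOVA uses baseline MMSE-2 only as a covariate. The slope analysis is by treatment group only.

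The visits left out are the two end-of-course assessments. By the Schedule of Activities, Week 13 (Day 91) is 14 days after dose 7 (Day 77), and Week 28 (Day 196) is 14 days after dose 14 (Day 182). The planned band visits are mid-course (Weeks 9, 20, 24) or 28 days after the last dose (Week 30, Day 210).

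The upper band is also where earlier evidence is thinnest. The two earlier repeated-dose Alzheimer's trials, NTRP101-202 and NTRP101-203, used strata 4-9 and 10-15, so scores 16, 17 and 18 are new. NTRP101-201 enrolled MMSE 14-26, but it gave a single dose to nine subjects and the SIB is not among its listed measures. A reader of a Week 28 result will ask how it looks in each band. Without a planned estimate, the answer will be post hoc.

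**Working it through.** **1. Visit lists for the band endpoint**

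| Place | Weeks | Week 13 | Week 28 |
|---|---|---|---|
| Protocol synopsis | 9, 20, 24, 30 | no | no |
| Protocol 4.3.3 | 9, 13, 20, 24, 30 | yes | no |
| Protocol 9.5.4, heading | 5, 9, 15, 20, 24 | no | no |
| Protocol 9.5.4, text | 9, 20, 24, 30 | no | no |
| SAP 3.2 | 5, 9, 13, 15, 20, 24 | yes | no |
| SAP 6.11.4.4 | 9, 20, 24, 30 | no | no |
| SAP section 9 item 2, endpoint as restated | 5, 9, 13, 15, 20, 24 | yes | no |
| SAP section 9 item 2, changed from | 9, 15, 20, 24 | no | no |
| SAP section 9 item 2, changed to | 9, 20, 24, 30 | no | no |
| SAP Table 14.2.2.4 | 9, 20, 24, 30 | no | no |

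Week 28 is in 0 of 10. Week 13 is in 3 of 10, all of them endpoint wording and none an analysis or table. The starting list in SAP section 9 item 2 does not match the endpoint that the same item restates, so the loss of Week 13 is not accounted for. SIB is collected at both visits (Protocol 6.1.10 and 6.1.18).

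**2. What the SAP model returns for the bands**

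With the band as a fixed effect only, the treatment difference at time t is a + b·t in both bands. A simulation of 300 trials used 50 patients per arm split equally between bands, SD 5.3, correlation 0.5 between visits, and a true Week 28 effect of 0 in band 10-14 and 4 in band 15-18.

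- Band as fixed effect only: one common Week 28 effect, mean 2.04.
- With band-by-time, treatment-by-band and treatment-by-band-by-time terms: means -0.02 (band 10-14) and 4.09 (band 15-18).

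**3. Precision of a Week 28 band estimate**

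The plan's own power figure comes first. Eq 1 solved for power is Φ(√[m·n·s²·d² / (2σ²(1-ρ))] - 1.96). With m = 50, n = 8, s² = 127, d = 0.15, σ = 5.3 and ρ = 0.5, the ratio is 1143/28.09 = 40.69, its root 6.38, and power exceeds 99.99%. With m = 40 it is 99.99%. The stated figure of more than 99% reproduces, but it concerns the whole-population slope, not a band at one visit.

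For a band, take the SD of change as σ√(2(1-ρ)) = 5.3 × √1 = 5.3. Then SE = SD·√(2/m), half-width = 1.96·SE, and power for 4 points = Φ(4/SE - 1.96). The documents give no band sizes, so the shares are assumptions.

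| Band share of 50 per arm | m | Half-width | Power | m with 20% dropout | Half-width | Power |
|---|---|---|---|---|---|---|
| 30% | 15 | 3.79 | 54% | 12 | 4.24 | 46% |
| 50% | 25 | 2.94 | 76% | 20 | 3.28 | 67% |
| 70% | 35 | 2.48 | 88% | 28 | 2.78 | 81% |

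With 25 per arm, no dropout and an assumed SD of 7.5 or 10, the half-width is 4.16 or 5.54 and power 47% or 29%.

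The difference between bands is less precise. With 25 per arm per band and SD 5.3, SE = √2 × 1.50 = 2.12, giving a half-width of about 4.2.

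**The case against.** The strongest reply is that the Week 28 figure is already implied. The model uses every visit from Week 5 to Week 30 and treats time as a straight line. If band-specific lines were fitted, the Week 28 estimate would be exactly 1/3 of Week 24 plus 2/3 of Week 30, and Week 13 would be 7/11 of Week 9 plus 4/11 of Week 20. This stands as arithmetic, and it rules out a stronger reading that someone might infer: that Week 28 data are discarded, or that the effect in the upper band cannot be recovered there. But it presupposes band-specific treatment terms, which SAP 6.11.4.4 does not include. It also leaves the reader to derive a figure that the plan could simply state.

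One could argue that reusing the primary model brings its comparison at every visit with it. SAP 6.11.4.4 and the title of Table 14.2.2.4 limit the output to four weeks, so this is not a safe reading.

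Some of the list conflict is old text. Protocol Appendix 3 records removal of Weeks 5 and 15 and the addition of Week 30, and the SAP takes precedence over the protocol. This explains the 9.5.4 heading and most of SAP 3.2, but not the loss of Week 13.

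The SAP allows extra tables in the study report if they are justified. That is true, but such tables would not be prespecified.

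Finally, this is one secondary endpoint in a phase 2 trial, randomisation is stratified on SIB rather than MMSE-2, and precision is modest. All of this stands and limits the weight of the point.

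**Conclusion.** The point holds as a gap in prespecified reporting. No planned analysis gives a treatment difference by MMSE-2 band at Week 28, and Week 13, a band endpoint in both documents, has no matching SAP analysis or table. The visit lists conflict and need reconciling in any case. Read literally, the SAP model gives no band-specific treatment effect at any visit, although Protocol 9.5.4 intends estimates within each band.

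A reader might go further and infer that the primary conclusion is weakened, or that the bands are the trial's main clinical question. The documents support neither. The primary test and sample size do not depend on the bands, and no section gives them that standing. That the 15-18 band is mostly new rests on counting scores (three of four), since no patient distribution is given.

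A Week 28 band result would be descriptive. Its half-width is about 2.5 to 3.8 points if a band holds 70% to 30% of each arm with SD 5.3 and no dropout, and about 4.2 to 5.5 with an assumed SD of 7.5 to 10 and 25 per arm. At the wider end it could not separate 0 from 4 points, and the contrast between bands is weaker still.

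**What to change.** Before unblinding:

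1. In SAP 6.11.4.4, add treatment-by-band and treatment-by-band-by-time terms, with the lower-order band-by-time term, or fit the model separately in each band.
2. In SAP 6.11.4.4 and Table 14.2.2.4, report the treatment difference with its 95% confidence interval in each band at Weeks 9, 13, 20, 24, 28 and 30. Name Week 28 as the main band result.
3. Report the same from the categorical-visit sensitivity model, so that the Week 28 figure does not rest only on the straight-line assumption.
4. Use this one list in SAP 3.2 and section 9 and in the Protocol synopsis, 4.3.3 and 9.5.4, and correct the count of time points in 9.5.4.
5. State that the band results are descriptive. SAP section 9 has removed false discovery rate control for secondary endpoints.

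Cost: changes to wording and model code, with no new data or visits. The downside is a few more secondary estimates: two further visits in each of two bands from the main model, plus the categorical-visit version.
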